5.8 Premature Termination or Suspension of Study

This study may be temporarily suspended or prematurely terminated if there is sufficient reasonable cause. Written notification, documenting the reason for study suspension or termination, will be provided by the suspending or terminating party to investigator, IND/IDE sponsor and regulatory authorities. If the study is prematurely terminated or suspended, the PI will promptly inform the IRB and will provide the reason(s) for the termination or suspension.

Circumstances that may warrant termination or suspension include, but are not limited to:

- Determination of unexpected, significant, or unacceptable risk to participants
- Demonstration of efficacy that would warrant stopping
- Insufficient compliance to protocol requirements •
- Data that are not sufficiently complete and/or evaluable
- Determination of futility
- Sponsor determination

Study may resume once concerns about safety, protocol compliance, data quality are addressed and satisfy the sponsor, IRB and/or FDA.

Study Agent (Study drug, device, biologic, vaccine etc.) and/or 6 **Procedural Intervention**

6.1 Study Agent(s) Description

Product: AT-001 500mg capsule for oral administration Dosage: 1,500mg (3X500mg capsules) twice daily Mode of Administration: Oral Compound:

Please see attached Sponsor pharmacy manual for additional details.

6.1.1 Acquisition

Investigational product will be shipped by the Sponsor and IND holder Applied Therapeutics Inc

CONFIDENTIAL

This material is the property of the NYU School of Medicine and Langone Medical Center. Do not disclose or use except as authorized in writing by the study sponsor

6.1.2 Formulation, Appearance, Packaging, and Labeling

AT-001 drug product is provided as AT-001 powder in a capsule in a 500 mg strength, packaged in blister cards. There are no excipients used in the manufacture of AT-001 powder in capsule, and no materials of human or animal origin are present. The white, opaque capsule shells contain hypromellose and titanium dioxide.

6.1.3 Product Storage and Stability

The product is stable at room temperature

6.1.4 Preparation

None

6.1.5 Dosing and Administration

Three 500 mg capsules (1500 mg) twice daily

6.1.6 Route of Administration

Oral. For subjects unable to swallow capsules, the capsules will be opened to allow mixing with soft foods, or mixed with water for nasogastric tube administration.

6.1.7 Duration of Therapy

Up to 14 days per discretion of the investigators and treatment team

6.1.8 Tracking of Dose

Dosing will be tracked in EPIC per hospital nursing and pharmacy protocol

6.2 Study Agent Accountability Procedures

The investigational pharmacy will track Investigational product

7 Study Procedures and Schedule

7.1 Study Procedures/Evaluations

7.1.1 Study Specific Procedures

Study procedures include data collection from the electronic medical record. The data collection will be performed by automated data extraction and chart review, and will be recorded on deidentified electronic case report forms (see Appendix for eCRF).

7.1.2 Standard of Care Study Procedures

All participants will receive standard of care for COVID-19 infection. This includes supportive measures for symptomatic relief, assisted ventilation including use of sedatives, pharmacological management of shock, organ injury, co-morbid bacterial infections, and co-morbid conditions.

7.2 Laboratory Procedures/Evaluations

7.2.1 Clinical Laboratory Evaluations

Standard of care laboratory procedures will be performed; results will be recorded in the research database There are no study-related laboratory evaluations.

- **Hematology:** hemoglobin, hematocrit, white blood cells (WBC) with differential count, platelet count.
- **Biochemistry:** serum electrolytes, blood urine nitrogen, creatinine, total bilirubin, alanine aminotransferase (ALT), aspartate aminotransferase (AST), albumin, total protein, calcium, magnesium, phosphate, troponin-I, brain natriuretic peptide, ferritin, CRP, ESR, IL-6, .
- **Urinalysis:** dipstick urinalysis, including protein, hemoglobin and glucose; if dipstick is abnormal, complete urinalysis with microscopic evaluation is required.
- **Pregnancy test**, usually to be done within 24 hours prior to study intervention and results must be available prior to administration of study product.

7.3 Study Schedule

Registry Study: All clinically-derived data on the attached eCRF will be collected on a daily basis until hospital discharge, or first 30 days of hospitalization (whichever is shorter).

Interventional study: All clinically-derived data on the attached eCRF will be collected on a daily basis during IP administration, with safety monitoring continuing 30 days after last dose of IP. In additional the following study procedures will be performed:

7.3.1 Enrollment/Baseline

Enrollment/Baseline Visit (Visit 1, Day 0)

- Obtain informed consent for potential participant (or their LAR) verified by signature on study informed consent form.
- Verify inclusion/exclusion criteria.
- See electronic case report form. These data will be collected at baseline.
- Start study drug administration
- Safety monitoring

7.3.2 Daily Interventional Study Visits (up to 14 days)

- See electronic case report form. These data will be collected daily.
- Study drug administration
- Safety monitoring

CONFIDENTIAL

This material is the property of the NYU School of Medicine and Langone Medical Center. Do not disclose or use except as authorized in writing by the study sponsor

7.3.3 Final Study Visit

• Safety monitoring for 30 days after last dose of IP

7.3.4 Withdrawal/Early Termination Visit

See electronic case report form

7.4 Concomitant Medications, Treatments, and Procedures

All concomitant prescription medications taken during study participation will be recorded on the case report forms (CRFs). For this protocol, a prescription medication is defined as a medication that can be prescribed only by a properly authorized/licensed clinician. Medications to be reported in the CRF are concomitant prescription medications, over-the-counter medications and non-prescription medications.

7.4.1 Precautionary Medications, Treatments, and Procedures

None

7.5 Prohibited Medications, Treatments, and Procedures

Other investigational medications

7.6 Prophylactic Medications, Treatments, and Procedures

None

7.7 Rescue Medications, Treatments, and Procedures

None

7.8 Participant Access to Study Agent at Study Closure

None

8 Assessment of Safety

8.1 Specification of Safety Parameters

All subjects in the interventional study will be observed daily by the treatment team for detection of adverse events.

8.1.1 Definition of Adverse Events (AE)

An *adverse event* (AE) is any symptom, sign, illness or experience that develops or worsens in severity during the course of the study. Intercurrent illnesses or injuries should be regarded as adverse events. Abnormal results of diagnostic procedures are considered to be adverse events if the abnormality:

- results in study withdrawal
- is associated with a serious adverse event
- is associated with clinical signs or symptoms
- leads to additional treatment or to further diagnostic tests
- is considered by the investigator to be of clinical significance

8.1.2 Definition of Serious Adverse Events (SAE)

Serious Adverse Event

Adverse events are classified as serious or non-serious. A *serious adverse event* is any AE that is:

- fatal
- life-threatening
- requires or prolongs hospital stay
- results in persistent or significant disability or incapacity
- a congenital anomaly or birth defect
- an important medical event

Important medical events are those that may not be immediately life threatening, but are clearly of major clinical significance. They may jeopardize the subject, and may require intervention to prevent one of the other serious outcomes noted above. For example, drug overdose or abuse, a seizure that did not result in in-patient hospitalization, or intensive treatment of bronchospasm in an emergency department would typically be considered serious.

All adverse events that do not meet any of the criteria for serious should be regarded as *non-serious adverse events*.

8.1.3 Definition of Unanticipated Problems (UP)

Unanticipated Problems Involving Risk to Subjects or Others

Any incident, experience, or outcome that meets all of the following criteria:

- Unexpected in nature, severity, or frequency (i.e. not described in study-related documents such as the IRB-approved protocol or consent form, the investigators brochure, etc)
- Related or possibly related to participation in the research (i.e. possibly related means there is a reasonable possibility that the incident experience, or outcome may have been caused by the procedures involved in the research)

CONFIDENTIAL

This material is the property of the NYU School of Medicine and Langone Medical Center. Do not disclose or use except as authorized in writing by the study sponsor

• Suggests that the research places subjects or others at greater risk of harm (including physical, psychological, economic, or social harm).

8.2 Classification of an Adverse Event

8.2.1 Severity of Event

For AEs not included in the protocol defined grading system, the following guidelines will be used to describe severity.

- **Mild** Events require minimal or no treatment and do not interfere with the participant's daily activities.
- **Moderate** Events result in a low level of inconvenience or concern with the therapeutic measures. Moderate events may cause some interference with functioning.
- Severe Events interrupt a participant's usual daily activity and may require systemic drug therapy or other treatment. Severe events are usually potentially life-threatening or incapacitating.

8.2.2 Relationship to Study Agent

The clinician's assessment of an AE's relationship to study agent (drug, biologic, device) is part of the documentation process, but it is not a factor in determining what is or is not reported in the study. If there is any doubt as to whether a clinical observation is an AE, the event should be reported. All AEs must have their relationship to study agent assessed. In a clinical trial, the study product must always be suspect. To help assess, the following guidelines are used.

- **Related** The AE is known to occur with the study agent, there is a reasonable possibility that the study agent caused the AE, or there is a temporal relationship between the study agent and event. Reasonable possibility means that there is evidence to suggest a causal relationship between the study agent and the AE.
- **Not Related** There is not a reasonable possibility that the administration of the study agent caused the event, there is no temporal relationship between the study agent and event onset, or an alternate etiology has been established.

8.2.3 Expectedness

The PI will be responsible for determining whether an AE is expected or unexpected. An AE will be considered unexpected if the nature, severity, or frequency of the event is not consistent with the risk information previously described for the study agent.

8.3 Time Period and Frequency for Event Assessment and Follow-Up

The occurrence of an AE or SAE may come to the attention of study personnel during study visits and interviews of a study participant presenting for medical care, or upon review by a study monitor. All AEs including local and systemic reactions not meeting the criteria for SAEs

will be captured on the appropriate RF. Information to be collected includes event description, time of onset, clinician's assessment of severity, relationship to study product (assessed only by those with the training and authority to make a diagnosis), and time of resolution/stabilization of the event. All AEs occurring while on study must be documented appropriately regardless of relationship. All AEs will be followed to adequate resolution.

Any medical condition that is present at the time that the participant is screened will be considered as baseline and not reported as an AE. However, if the study participant's condition deteriorates at any time during the study, it will be recorded as an AE. UPs will be recorded in the data collection system throughout the study.

Changes in the severity of an AE will be documented to allow an assessment of the duration of the event at each level of severity to be performed. AEs characterized as intermittent require documentation of onset and duration of each episode.

The PI will record all reportable events with start dates occurring any time after informed consent is obtained until 7 (for non-serious AEs) or 30 days (for SAEs) after the last day of study participation. At each study visit, the investigator will inquire about the occurrence of AE/SAEs since the last visit. Events will be followed for outcome information until resolution or stabilization.

All unresolved adverse events should be followed by the investigator until the events are resolved, the subject is lost to follow-up, or the adverse event is otherwise explained. At the last scheduled visit, the investigator should instruct each subject to report any subsequent event(s) that the subject, or the subject's personal physician, believes might reasonably be related to participation in this study. The investigator should notify the study sponsor of any death or adverse event occurring at any time after a subject has discontinued or terminated study participation that may reasonably be related to this study. The sponsor should also be notified if the investigator should become aware of the development of cancer or of a congenital anomaly in a subsequently conceived offspring of a subject that has participated in this study.

8.4 Reporting Procedures – Notifying the IRB

8.4.1 Adverse Event Reporting

Adverse events that do not meet criteria for serious adverse event or unanticipated event will be submitted at the time of study continuation or termination, whichever occurs first.

8.4.2 Serious Adverse Event Reporting

According to CFR 21 CFR 312.32(c)(1), "the sponsor must notify FDA and all participating investigators in an IND safety report of potential serious risks, from clinical trials or any other source, as soon as possible, but in no case later than 15 calendar days after the sponsor determines that the information qualifies reporting. In each IND safety report, the sponsor must identify all IND safety reports previously submitted to FDA concerning a similar suspected

adverse reaction, and must analyze the significance of the suspected adverse reaction in light of previous, similar reports or any other relevant information. The sponsor must report any suspected adverse reaction that is both serious and unexpected. The sponsor must report an adverse event as a suspected adverse reaction only if there is evidence to suggest a causal relationship between the drug and the adverse event, such as:

(A) A single occurrence of an event that is uncommon and known to be strongly associated with drug exposure (e.g., angioedema, hepatic injury, Stevens-Johnson Syndrome);
(B) One or more occurrences of an event that is not commonly associated with drug exposure, but is otherwise uncommon in the population exposed to the drug (e.g., tendon rupture);
(C) An aggregate analysis of specific events observed in a clinical trial (such as known consequences of the underlying disease or condition under investigation or other events that commonly occur in the study population independent of drug therapy) that indicates those events occur more frequently in the drug treatment group than in a concurrent or historical control group."

Furthermore, according to 21 CFR 312.32(c)(2), "the sponsor must also notify FDA of any unexpected fatal or life-threatening suspected adverse reaction as soon as possible but in no case later than 7 calendar days after the sponsor's initial receipt of the information."

8.4.3 Unanticipated Problem Reporting

Incidents or events that meet the OHRP criteria for UPs require the creation and completion of an UP report form. It is the site investigator's responsibility to report UPs to their IRB and to the DCC/study sponsor. The UP report will include the following information:

- Protocol identifying information: protocol title and number, PI's name, and the IRB project number;
- A detailed description of the event, incident, experience, or outcome;
- An explanation of the basis for determining that the event, incident, experience, or outcome represents an UP;
- A description of any changes to the protocol or other corrective actions that have been taken or are proposed in response to the UP.

To satisfy the requirement for prompt reporting, UPs will be reported using the following timeline:

- UPs that are SAEs will be reported to the IRB and to the study sponsor within 24 hours of the investigator becoming aware of the event.
- Any other UP will be reported to the IRB and to the study sponsor within 72 hours of the investigator becoming aware of the problem.
- All UPs should be reported to appropriate institutional officials (as required by an institution's written reporting procedures) within 72 hours of the IR's receipt of the report of the problem from the investigator.

8.4.4 Reporting of Pregnancy

Pregnancy will be considered an unanticipated event and will be reported to the IRB and Sponsor within 24 hours.

CONFIDENTIAL

This material is the property of the NYU School of Medicine and Langone Medical Center. Do not disclose or use except as authorized in writing by the study sponsor

8.6 Study Halting Rules

Administration of study agent will be halted when three grade 3 AEs determined to be "probably related" are reported to the Sponsor.

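### The only numeric halting rule (section 8.6) counts AEs by a grade and a causality category that the protocol's own AE classification (section 8.2) does not define

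*Combined protocol and SAP*

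**What the plan says.** Section 8.6 consists of one sentence: "Administration of study agent will be halted when three grade 3 AEs determined to be 'probably related' are reported to the Sponsor". It names a count (three), a severity grade and a causality category.

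Severity is classified in section 8.2.1, which opens: "For AEs not included in the protocol defined grading system, the following guidelines will be used to describe severity". The guidelines that follow have three levels: Mild, Moderate and Severe. Of the top level the section says: "Severe events are usually potentially life-threatening or incapacitating". No numbered grades appear there or elsewhere in the protocol text.

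Causality is classified in section 8.2.2, which requires: "All AEs must have their relationship to study agent assessed". It offers two categories. An AE is Related if it is known to occur with the agent, or "there is a reasonable possibility that the study agent caused the AE, or there is a temporal relationship between the study agent and event". It is Not Related if there is no reasonable possibility of causation, or "there is no temporal relationship between the study agent and event onset, or an alternate etiology has been established". There is no 'probably related' level.

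Section 8.3 says that the clinician's severity assessment and the relationship to study product are collected for each AE. It adds no scale for either.

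**The concern.** A halting rule protects participants only if the person counting can tell from the record whether an event counts. Here the rule uses two terms that occur nowhere else in the protocol, and the classification meant to supply them uses different terms.

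Safety is the primary endpoint of the interventional trial (section 4.2.1), and section 8.6 is its only numeric stopping threshold. Section 8.7 places oversight with the PI and sponsor, names no independent board, and expects many organ-dysfunction and septic-shock events. Those are the events for which grade and cause are hardest to judge. The drug's listed potential risks include hepatic toxicity, renal toxicity and hypotension, and section 2.4.1 expects liver and kidney failure and hypotension from COVID-19 itself. The unclear boundary therefore falls on events the trial expects to see. If the meaning of the rule is not fixed beforehand, it may have to be settled once events have occurred.

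**Working it through.** There is no planned figure to reproduce. The threshold of three is given without a derivation or operating characteristic, the sample of 20 is a convenience sample (section 10.5), and there is no hypothesis test (section 10.2). The check is therefore a comparison of the text, with no event rates assumed.

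**Step 1: set the terms side by side.**

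| Element | Section 8.6 counts | Section 8.2 defines |
|---|---|---|
| Severity | 'grade 3' | Mild, Moderate, Severe (8.2.1) |
| Causality | 'probably related' | Related, Not Related (8.2.2) |

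Section 8.2 yields 3 severity levels x 2 causality categories = 6 combinations. The number labelled both 'grade 3' and 'probably related' is 0. This counts labels only and says nothing about how often the difference would matter.

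**Step 2: severity.** Section 8.2.1 presents its three levels as a fallback for AEs outside a protocol-defined grading system, but the protocol text contains no such system. The natural mapping is that grade 3 means Severe, the third and top level, which would include the worst events. The rule does not say so, and it says 'grade 3' rather than 'grade 3 or higher'. Take three life-threatening AEs that were probably caused by the drug:
- If grade 3 means Severe, the count is 3 and dosing halts.
- If grade 3 is literal and the absent system puts such events in a higher grade (an assumption), the count is 0 and dosing continues.

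**Step 3: causality.** Under section 8.2.2 a reasonable possibility, or a temporal relationship alone, is enough for Related. Section 8.1.3, writing about research procedures, uses the same phrase to explain the weaker term: "possibly related means there is a reasonable possibility that the incident experience, or outcome may have been caused by the procedures". Related therefore runs from possible to probable, and nothing in sections 8.2 or 8.3 marks off the probable part. Take three Severe AEs with only a temporal link to dosing:
- If 'probably related' is read as Related, the count is 3 and dosing halts.
- If 'probably related' is a higher bar, the count is 0 and dosing continues.

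**Step 4: look for a reconciliation elsewhere.** Sections 2.4.1 and 8.7 say how drug-related AEs are to be identified: by timing, by plausibility or known class risks, or by magnitude or duration beyond that expected from COVID-19. Timing is again one of several alternatives, and no 'probably' level is defined. Section 5.8 lists qualitative grounds for suspension without counts. None of these sections resolves steps 2 and 3.

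**Side note.** Within section 8.2.2, an on-treatment event with an established other cause meets one criterion for Related (timing) and one for Not Related (alternate etiology), and no precedence is stated. This bears on section 8.6 only if 'probably related' is read as Related. On an ordinary reading of 'probably', such an event would not count.

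**The case against.** The strongest reply is that an ordinary reading makes the rule workable: grade 3 is the third and top level, Severe, and 'probably related' means likely to be drug-caused. The life-threatening events in step 2 then count, and the temporal-only events in step 3 do not. That is sensible and may be what was intended, but the protocol does not state it. On causality it also needs a judgement that neither section 8.2.2 nor section 8.3 asks the clinician to make.

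A second reply is that a scale may sit in the eCRF, the manual of procedures, the safety-monitoring plan or the sponsor's emergency use IND protocol. None of these was available, so this may be true. However, sections 8.2 and 8.6 cite none of them for a scale. Section 19 says that its attachments, which include the eCRF and that IND protocol, are not part of the protocol and can change without an amendment. A severity scale found there would also leave the two-level causality classification in section 8.2.2 unchanged.

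A third reply is that other protections stand behind the rule:
- AEs are documented regardless of relationship (8.3).
- Deaths and immediately life-threatening events reach the sponsor within 24 hours (8.5).
- Clinical data are reviewed daily, with a full case review after 7 and 14 days (8.7).
- Study drug can be stopped for treatment-related AEs (2.4.1), and the study can be suspended (5.8).

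This stands and lowers the seriousness of the point, although none of these sets a threshold.

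A reader might infer more than the documents support:
- **That the rule leaves out deaths and life-threatening events.** This follows only if the unseen grading system has grades above 3. The visible text leans the other way, because its top level covers potentially life-threatening events.
- **That the study has no usable scale.** The unseen documents may hold one.
- **That the meaning will be chosen after events occur.** That is a risk, and nothing in the documents shows it.

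**Conclusion.** The point holds as a mismatch of terms with practical consequences. As written, the rule in section 8.6 cannot be applied from the categories in section 8.2. The causality gap is the firmer part, because Related has no 'probably related' subset. The severity gap is narrower: a literal 'grade 3' does not clearly include life-threatening or fatal events, and whether it excludes them depends on a grading system that is not in the text.

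The effect on the probability of halting cannot be given, because the documents state no AE rates. Steps 2 and 3 show only that the reading can change a count from 3 to 0. No analysis or estimate is affected, since the interventional trial is descriptive. Given that and the other safeguards, this is a should-fix point. It rests on the protocol text alone. A scale in an unseen document would weaken the severity part, and would weaken the causality part only if it also defined 'probably related'.

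**What to change.** Use one set of terms throughout:
- In section 8.2.1, add the numbered severity grades, so that the reference to a protocol-defined system points to something. If a scale already exists in another study document, put it in section 8.2 itself.
- In section 8.2.2, add a causality scale with a defined 'probably related' level.
- Collect both on the eCRF.
- Reword section 8.6 to: halted when three AEs of grade 3 or higher (including life-threatening and fatal events) judged probably related are reported to the Sponsor.

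This keeps the sponsor's count and causality bar. Rewriting section 8.6 as three Severe, Related AEs would look simpler, but it would lower the bar to any temporal relationship. Among hospitalized COVID-19 patients that would be a different rule.

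As a separate tidy-up, section 8.2.2 could state which criterion prevails when timing and an alternate etiology are both present.

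The cost is a protocol wording change in sections 8.2.1, 8.2.2 and 8.6 and a matching eCRF change, with no new visits, procedures or participants. The rule may fire slightly earlier than under a literal 'grade 3', because higher-grade events would clearly count.
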